#### **4.5.2 Phase 2: At-home study**

After enrollment and collection of baseline data, subjects will switch from their personal t:slim X2 insulin pump with Control-IQ technology to the t:slim X2 study pump with Control-IQ Pro v2.0. Subjects will receive training on all of the new features and the instructions for using them during the following week of the study. Subjects will keep a log of their use of the required features of the new pump for the week. Subjects will be required to attend the study site visit each week (+/- 3 days), during which time their pump and CGM data will be downloaded and they will receive instructions for the following week.

Remote real-time monitoring using the Dexcom G6 app will be required to be shared by subjects with their local contact(s) throughout the study, and with study staff for the first 10 subjects. After the first 10 subjects complete the study, required real-time alerts to study providers may be removed for future subjects after sponsor review and approval. This review will certify that:

- 1) No severe hypoglycemia events related to algorithm delivered automated insulin dosing occur that required study staff intervention because the subject was not aware/treating appropriately in the first 10 subjects.
- 2) No severe hyperglycemic events related to algorithm delivered automated insulin dosing occurred that required study staff intervention because the subject was not aware/treating appropriately in the first 10 subjects.

During the weekly required visit, the Control-IQ software in their pump will be reconfigured to support the following week's features. The configuration tool will be run by clinical staff from an approved study laptop, using Bluetooth to reconfigure the pump. If a software update to the pump is not required at the weekly visit, and the subject is able to download their pump remotely, the visit may be performed remotely per investigator discretion.

After each weekly download, staff will review the download to document correct use of each feature, and document this on the study CRF. If a subject is using a feature not per the study instructions (for example, using eating soon not just prior to meals), subjects will be re-educated

on the relevant instructions and this will be documented in the study CRF. All subjects will receive a phone call 48 hours (+/- 1 day) after each weekly feature update to review any new questions that may arise.

The feature use will be randomized per subject. The feature schedule is outlined below in **Table 4**:

**Table 4:** Schedule of prescribed use of standard vs. new features.

*Participants will be sorted into cohorts. Each cohort will be randomly assigned the order in which they complete weeks A-D.*

| Study Period                        | Normal Activity Setting                             | Exercise Setting                              | Eating Soon  | Late Meal Bolus     |
|-------------------------------------|---|---|--|---------------------|
| Baseline                     | Standard  | Standard                                      | N/A  | N/A                 |
| 2-day Supervised/Hotel Study | Lower Target
Auto-bolus on
Use while sleeping | Auto-Bolus Off x 2 required exercise sessions | Use once ~1 hour to meal

Use once for 3 consecutive hours prior to a meal | One time            |
| Week A                       | Lower Target
Auto-bolus on                       | Auto-bolus off                                | 40-60 minutes before every meal  | Directed not to use |
| Week B                       | Lower Target
Auto-bolus off                      | Auto-bolus off                                | 40-60 minutes before every meal  | Directed not to use |
| Week C                       | Lower Target
Auto-bolus on                       | Auto-bolus off                                | As needed  | As needed           |
| Week D                       | Standard Target
Auto-bolus on                    | Auto-bolus off                                | As needed  | As needed           |

Prior to sending any subject home with the study device, study staff will assure the following safety instructions are reviewed with subjects as part of device training:

- 1) Completion of the study device training form, reviewing the new features of Control-IQ 2.0 and their required use.
- 2) Study subjects will be given a logbook to record use of the late bolus feature, to record the time they ate their meal relative to pressing the late bolus feature button, as well as to record start and end of exercise.

- 3) Subject will be asked to set-up/re-enable sleep schedules after lunch if they desire, or may continue to use the normal activity setting overnight with the required targets per each week of the study.
- 4) Study staff will collect names and phone numbers for 1-2 local personal contacts in case a participant cannot be reached during the study period. If the participant lives alone, they must have a contact who lives within 30 minutes of them.
- 5) Staff will review the outpatient hyper- and hypoglycemia treatment plans (Section 7.9 and 7.10) and expectations for real-time monitoring with each subject.

**Observation and Recording of Adverse Events:** Subjects will be required to report AEs. Open-ended questions and questions specific to SH and DKA will be included in all subject visits. An AE form will be completed for every adverse event reported by a subject. Any medical management of an event and the resolution of the event must be recorded in source documentation and on the appropriate eCRF using medical terminology.

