### 2.2 Study Design

This feasibility study is a prospective, crossover study with a 48-hour supervised hospital phase, followed by a 4-week home study with sequential interventions (new features) and remote monitoring. Up to 110 subjects may sign the consent form and be screened, so that a maximum of 90 subjects (up to 30 subjects to wear the study device, and up to 60 personal contacts) may be enrolled. Subjects wearing the device will be both male and female, aged 14 and up, inclusive, who have used Control-IQ in closed-loop at least 80% of the 2-week time period before enrollment. Approximately 5 subjects will be enrolled in the initial 48-hr hospital phase. Approximately 25 additional subjects will be enrolled to participate in the at-home study. Each subject will use all features (current and new) and therefore will act as his/her own comparator. Remote real-time monitoring using the Dexcom G6 app will be required to be shared with their local contact(s) throughout the study, and with study staff for the first 10 subjects. After the first 10 subjects complete the study, required real-time alerts to study providers may be removed for future subjects after sponsor review and approval. Subjects will continue to share with their personal contacts.

The data collected in this study will be directly entered into an electronic data capture system (EDC) using electronic case report forms (eCRFs) when possible. Paper source may also be used. Subject data will include demographics, focused medical history, therapy data, and baseline and follow-up measures.

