## 5. STATISTICAL CONSIDERATIONS

### 5.1 Statistical Analysis:

This feasibility study is a prospective, crossover 5-week home study with sequential interventions (new features). Each subject will use all features (current and new) and therefore will act as his/her own comparator (paired data points). The study is designed to obtain a primary safety profile on new feature configuration

Descriptive statistics of the rates of significant hypoglycemia (< 54 mg/dl), severe hypoglycemia, DKA, and serious adverse events will be reported for baseline and each intervention configuration. Additionally, descriptive statistics of glycemic outcomes will for baseline and each intervention configuration will be provided. The statistics will include:

- % time < 54 mg/dl median and interquartile range
- Number of events of severe hypoglycemia (needing assistance) and percent of individuals experiencing at least one event of severe hypoglycemia.
- Number of events of DKA and percent of individuals experiencing at least one DKA event.
- Rate of serious adverse events per 100 patient years.
- % time < 70 mg/d median and interquartile range
- % time > 250 mg/dl median and interquartile range
- % time between 70-180 mg/dl median and interquartile range
- % time between 70-140 mg/dL median and interquartile range
- Post-prandial glycemic peak median and interquartile range
- 4-hour post-meal glucose AUC median and interquartile range
- Median sensor glucose and interquartile range
- % time in automation median and interquartile range

These statistics will be calculated at the patient-level, and a sub-analysis of daytime vs. nighttime statistics will be provided.

Additionally, the distributions of glycemic outcomes for baseline and each intervention configuration will be depicted using boxplots. The individual-level difference between each intervention configuration and baseline will also be depicted using boxplots.

**Success Criteria / Goal:** The 48 hour observed session will be considered useful for data analysis if the subject has at least 75% CGM availability during the session.

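### The randomisation unit is given as both the subject and an undefined cohort; with few cohorts, configuration would be partly confounded with study week

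*Combined protocol and SAP*

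**What the plan says.** The text of section 4.5.2 that introduces Table 4 makes the subject the unit: "The feature use will be randomized per subject". The note under the table title makes it the cohort: "Participants will be sorted into cohorts. Each cohort will be randomly assigned the order in which they complete weeks A-D". No other section describes the cohorts, the generation of the order list or any balancing rule.

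Section 2.2 caps the study at "up to 30 subjects to wear the study device, and up to 60 personal contacts". It splits the device wearers in two: "Approximately 5 subjects will be enrolled in the initial 48-hr hospital phase", and "Approximately 25 additional subjects will be enrolled to participate in the at-home study". Every device wearer is to pass through all the configurations.

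Section 5.1 calls the study a crossover and says that each subject "will act as his/her own comparator (paired data points"). It plans medians, interquartile ranges, event counts and boxplots for baseline and for each configuration, plus boxplots of each configuration's individual difference from baseline. It plans no test and no period, sequence or cohort term. The synopsis rationale says that the results will help determine which features go into later trials and the commercial product.

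**The concern.** A randomisation list cannot be built from two statements that name different units. The choice also affects what the study can show. A crossover protects comparisons between configurations from learning and other week effects only if each configuration is spread evenly over the four weeks. Section 5.1 does not adjust for week, so the allocation of orders is the only protection.

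The protocol itself makes week effects plausible. Subjects are newly trained on the features, telephoned about 48 hours after each weekly update, and re-educated if a download shows misuse. Table 4 requires Eating Soon before every meal in Weeks A and B but leaves it to need in Weeks C and D, and no washout is described. Use in C or D may therefore depend on whether A or B came first.

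If a few cohorts each take one order, a configuration may fall mostly early or mostly late. Part of its apparent advantage or disadvantage would then be a week effect, in data meant to guide the choice of features.

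**Working it through.** **The plan's own figure.** There is no sample-size or power calculation to reproduce. The subject count agrees with itself: 5 + 25 = 30.

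**Inputs.** There are four configurations (A to D), hence 4! = 24 possible orders, and up to 30 device wearers (section 2.2). The number of cohorts K is not stated. I assume K from 2 to 10, cohorts of equal size, and one order drawn independently at random for each cohort. K = 30 stands for simple individual randomisation.

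**Step 1: imbalance in week position.** Take two configurations in one random order. Their positions form one of 4 × 3 = 12 equally likely ordered pairs. Differences of ±1, ±2 and ±3 weeks occur 6, 4 and 2 times, so the variance of the difference is (6×1 + 4×4 + 2×9)/12 = 40/12 = 3.33. Averaged over K units, SD = √(3.33/K).

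**Step 2: a configuration never used in the first week.** P = 1 − S(K)/4^K, where S(K) counts the ways in which K draws cover all four configurations. For K = 6 this is 1 − 1560/4096 = 62%.

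**Step 3: pairs always in the same order.** For one given pair, P = 2 × 0.5^K. For any of the six pairs, P was simulated with 40,000 draws.

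**Step 4: could a week adjustment rescue the comparison?** This is the chance that all contrasts among A to D are estimable after removing cohort and week effects, simulated with 1,000 draws.

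| K | SD of mean position difference (weeks) | Some configuration never first | Some pair always in same order | All week-adjusted contrasts estimable |
|---|---|---|---|---|
| 2 | 1.29 | 100% | 96% | 26% |
| 3 | 1.05 | 100% | 74% | 76% |
| 4 | 0.91 | 91% | 48% | 94% |
| 6 | 0.75 | 62% | 15% | 99% |
| 10 | 0.58 | 22% | 1% | 100% |
| 30 | 0.33 | below 0.1% | about 0 | 100% |

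Confounding with week is complete only for K = 1. Four independently drawn orders form a Latin square with probability 576/331,776 = 0.17%, so balance has to be designed in.

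**Step 5: from position to bias.** If an outcome drifts linearly by d per week, the unadjusted difference between two configurations is shifted by d times the realised mean position difference. A one-SD shift is 1.05d with 3 cohorts, 0.75d with 6 and 0.33d with 30 individuals. The documents give no value for d.

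**Step 6: the proposed sequences.** In ABDC, BCAD, CDBA and DACB, each configuration occurs once in each week. The adjacent pairs are AB, BD, DC; BC, CA, AD; CD, DB, BA; DA, AC, CB: all 12 ordered pairs, once each. Thirty is not a multiple of 4, so seven full blocks leave two subjects over. The largest position difference that two distinct sequences can add for any pair is 3 + 1 = 4 weeks in total (A against C, for example), so the residual mean imbalance is at most 4/30 = 0.13 week.

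**The case against.** The two statements might be reconciled. If cohorts are sequence groups, and subjects are sorted into them at random, then each subject is in effect randomised. Drawing the cohorts' orders from a balanced set would also fit the wording. This stands as a possibility, but the protocol says neither. It also means that a small number of cohorts, sequential enrolment of cohorts and unbalanced orders are assumptions.

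Week effects may be small. Subjects must have at least 3 months of Control-IQ experience and are trained on the new features before they start. This limits a learning effect but does not exclude one. In addition, with 6 cohorts week-adjusted contrasts are estimable about 99% of the time. That helps only an analysis that adjusts for week, which section 5.1 does not plan.

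The analysis is descriptive, and the one individual-level contrast specified is configuration against baseline. A reader might infer that cohort assignment invalidates the paired analysis through clustering. With no tests, confidence intervals or standard errors planned, that point has little force. Position imbalance still matters: within a subject the same baseline is subtracted from every configuration, so differences among the planned boxplots carry the week effects of the configurations.

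A reader might also infer that configuration is confounded with the monitoring regime, because staff receive real-time alerts for the first 10 subjects only. The documents do not support this. Alerts attach to the subject and may be removed only for later subjects, so each person has one regime through Weeks A to D. With full participation every configuration has the same monitored share, 10/30 = 33.3%, whatever the order. Only the sequence could line up with the regime.

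**Conclusion.** The contradiction about the randomisation unit is real, and nothing in the documents resolves it. Its consequence is conditional. If cohorts are the unit and are few, configuration is partly confounded with study week, and with calendar week only if each cohort runs together as a block. With an assumed 3 to 10 cohorts, the typical imbalance is about 1.7 to 3.2 times that of individual randomisation (0.58/0.33 and 1.05/0.33 by the table's formula, that is √(30/10) and √(30/3)).

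Two stronger readings go too far. One is that the design leaves only a few random units; the number of cohorts is unknown. The other is that configuration and week cannot be separated; that holds for certain only with a single cohort or identical orders, and its likelihood falls quickly as cohorts are added.

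The severity is moderate. This is a descriptive feasibility study with safety as its primary objective, and the size of any weekly drift is unknown. However, its results are meant to inform a choice among features, and the remedy is cheap.

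**What to change.** - In section 4.5.2, delete the cohort rule from the Table 4 note. State that each subject is individually randomised, in permuted blocks of 4, to one of four Williams-square sequences: ABDC, BCAD, CDBA or DACB. Stratifying by monitoring regime is not needed.
- In section 5.1, add a descriptive summary of the outcomes by study week and by sequence, so that a drift over weeks can be seen next to the comparison of configurations.

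The cost is a new randomisation list, a sentence and one extra set of summaries. Pumps are already reconfigured subject by subject at the weekly visits. The small downside is that staff could no longer train a whole cohort on one configuration.

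The change does not remove the time effect from comparisons of a configuration with baseline. Baseline always precedes Weeks A to D, and no ordering of those weeks alters that. The report should say so beside those boxplots.

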#### **4.6 Early Termination Visit (If Applicable)**

Participants will be asked to come for an end of study visit in the event of withdrawal or early termination.

#### **4.7 Unscheduled Visits**

Participants may have unscheduled visits during the study period if required for additional device training or other unanticipated needs per the study investigator discretion.

#### **4.8 Final Visit**

Subjects will return all study supplies and complete the system usability scale survey. All study devices (glucose meter, ketone meter, insulin pump and CGM) will be downloaded. Participants will be permitted to keep the blood glucometer, blood ketone meter and any remaining CGM sensors at the end of the study, but will need to return all other devices, including insulin pump and related supplies.

## 5. STATISTICAL CONSIDERATIONS

### 5.1 Statistical Analysis:

This feasibility study is a prospective, crossover 5-week home study with sequential interventions (new features). Each subject will use all features (current and new) and therefore will act as his/her own comparator (paired data points). The study is designed to obtain a primary safety profile on new feature configuration

Descriptive statistics of the rates of significant hypoglycemia (< 54 mg/dl), severe hypoglycemia, DKA, and serious adverse events will be reported for baseline and each intervention configuration. Additionally, descriptive statistics of glycemic outcomes will for baseline and each intervention configuration will be provided. The statistics will include:

- % time < 54 mg/dl median and interquartile range
- Number of events of severe hypoglycemia (needing assistance) and percent of individuals experiencing at least one event of severe hypoglycemia.
- Number of events of DKA and percent of individuals experiencing at least one DKA event.
- Rate of serious adverse events per 100 patient years.
- % time < 70 mg/d median and interquartile range
- % time > 250 mg/dl median and interquartile range
- % time between 70-180 mg/dl median and interquartile range
- % time between 70-140 mg/dL median and interquartile range
- Post-prandial glycemic peak median and interquartile range
- 4-hour post-meal glucose AUC median and interquartile range
- Median sensor glucose and interquartile range
- % time in automation median and interquartile range

These statistics will be calculated at the patient-level, and a sub-analysis of daytime vs. nighttime statistics will be provided.

Additionally, the distributions of glycemic outcomes for baseline and each intervention configuration will be depicted using boxplots. The individual-level difference between each intervention configuration and baseline will also be depicted using boxplots.

**Success Criteria / Goal:** The 48 hour observed session will be considered useful for data analysis if the subject has at least 75% CGM availability during the session.

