| Main Criteria for Exclusion             | 
Eligibility to enroll in the study will be assessed based on the following exclusion criteria:
 
 
1. Diabetic ketoacidosis (DKA) in the past 6 months and Severe hypoglycemia (needing assistance) in the past 6 months
 
2. Inpatient psychiatric treatment in the past 6 months
 
3. History of drug abuse (defined as any illicit drug use) or history of alcohol abuse prior to screening or unwillingness to agree to abstain from illicit drugs throughout the study.
 
4. History of heart, lung or kidney disease determined by investigator to interfere with the study
 
5. Use of glucocorticoids, beta blockers or other medications determined by investigator to interfere with study
 
6. Use of long-acting insulin or any non-insulin glucose lowering agents (i.e. SGLT-2 inhibitor) other than Metformin
 
7. Febrile illness within 3 days of the start of the study
 
8. Subject is pregnant or lactating or intending to become pregnant before or during participation in this study.
 
9. For subjects >50 years old or with diabetes duration >20 years and who are exercising as part of the 48 hour study, abnormal electrocardiogram consistent with increased risk of arrhythmia, ischemia, or prolonged QTc interval (> 450 ms)
 
10. Significant chronic kidney disease (eGFR < 60) or hemodialysis
 
11. Significant liver disease
 
12. History of adrenal insufficiency
 
13. History of abnormal TSH consistent with hypothyroidism or hyperthyroidism that is not appropriately treated
 
 |
| Procedures in Screening/Baseline Period | 
Baseline data will be collected. Mean/median sensor glucose, TIR and all glycemic outcomes will be recorded as baseline data from the use of Control-IQ in closed-loop at least 80% of the 2-week time period before the first visit timepoint.
  |
| Management of Adverse Events            | 
Safety information will be collected weekly during study clinic visits. The event, date of onset, severity, seriousness, duration and relationship to the device will be documented. All reported device-related AEs will be followed until they are adequately resolved or stabilized, or until study completion/termination, whichever comes first.
  |

|                      |  |
|----------------------|--|

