| Statistical Analysis | Descriptive statistics will be used to evaluate rates of AEs as well as glycemic outcomes after using existing Control-IQ system vs. new features. Each subject will use all features and therefore act as his/her own comparator. |
|----------------------|--|

127

128 The study will be conducted and documented in accordance with the US Federal and Local  
129 requirements for post-market human clinical studies, the protocol, and the stipulations of the  
130 clinical trial agreement.

131

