#### 3.1.2 Exclusion Criteria:

- 250 1) Diabetic ketoacidosis (DKA) in the past 6 months
- 251 2) Severe hypoglycemia (needing assistance) in the past 6 months
- 252 3) Inpatient psychiatric treatment in the past 6 months
- 253 4) History of drug abuse (defined as any illicit drug use) or history of alcohol abuse prior to
- 254 Screening or is unwilling to agree to abstain from illicit drugs throughout the study
- 255 5) History of heart, lung or kidney disease determined by the investigator to interfere with the study

- 256 6) Use of glucocorticoids, beta blockers or other medications determined by investigator to interfere  
257 with the study  
258 7) Use of long-acting insulin or any non-insulin glucose lowering agents (i.e. SGLT-2 inhibitor)  
259 other than metformin  
260 8) Use of Afrezza during the study period  
261 9) Febrile illness within 3 days of the start of the study  
262 10) Subject is pregnant or lactating or intending to become pregnant before or during participation in  
263 this study  
264 11) For subjects >50 years old or with diabetes duration >20 years who will be exercising as part of  
265 the 48 hour study, abnormal electrocardiogram consistent with increased risk of arrhythmia,  
266 ischemia, or prolonged QTc interval (> 450 ms)  
267 12) Significant chronic kidney disease (eGFR < 60) or hemodialysis  
268 13) Significant liver disease  
269 14) History of adrenal insufficiency  
270 15) History of abnormal TSH consistent with hypothyroidism or hyperthyroidism that is not  
271 appropriately treated  
272

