### 4.2 Enrollment procedure:

The potential study subjects will be recruited by the clinical site from among their current users of the t:slim X2 pump with Control-IQ technology. After a description of the study is provided by the investigator, the subject will be asked to sign the informed consent form (ICF). Assent will be obtained from subjects <18 years of age. The subject's local contact(s) must also sign the "Personal Contact Consent". Eligibility to enroll in the study will be assessed based on the inclusion/exclusion criteria. Use of Control-IQ in closed-loop at least 80% of the 2-week time period before enrollment is required and must be confirmed during the screening process. Enrollment information will be entered into the EDC system. In addition, demographic and relevant medical history will be collected at this time and entered into the eCRFs. The subject will be considered enrolled when the investigator attests that the subject meets all eligibility criteria on the study enrollment CRF.

All subjects will be required to use the Dexcom G6 app if not using already, and enable real-time alerts to followers. Study staff will collect names and phone numbers for 1-2 local personal contacts in case a participant cannot be reached during the study period. If the participant lives alone, they must have a contact who lives within 30 minutes of them.

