Sites visits may be remote if updating of pump firmware is not required at the visit, per investigator discretion.

316

Confidential

Contains trade secrets and/or confidential information exempt from disclosure from 21 CFR 20.61

**Baseline Data Collection:** Only Control-IQ users demonstrating use of Control-IQ in closed-loop at least 80% of the time during the 2 weeks before enrollment are eligible for the study. Data from the 2-week period before enrollment will serve as the baseline pump and CGM data.

**Subject Completion or Early Withdrawal:** The subject completes the study approximately 5 weeks after enrollment, or when they choose to withdraw from the study, if earlier than 5 weeks.

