## **4.5 Study Procedures**

### **4.5.1 Phase 1: 48-hr supervised study in-clinic/transitional environment:**

Approximately 5 subjects will be enrolled in Phase 1 of the study. The purpose of Phase 1 is to determine the safety of the Control-IQ Pro v2.0 system with use of the new features in a medically supervised, observed setting: 1) Lower target normal activity overnight and receiving auto-correction boluses, 2) Exercise Activity without autocorrections, and 3) Adjustments to meal bolusing.

After enrollment and collection of baseline data (use of the current standard Control-IQ commercial system for 1-3 weeks) subjects will be admitted in the evening and will switch from their personal t:slim X2 insulin pump with Control-IQ technology to the t:slim X2 study pump with Control-IQ Pro v2.0. Subjects will receive training on all of the new features and the instructions for using them during the ~48-hours of the study.

During this phase of the study, subjects will be remotely monitored by the study team, including a study physician, 24 hr per day. Pump and CGM alerts will be set to annunciate throughout the study. The study team will intervene if 1) CGM <70 mg/dL overnight, or 2) if a Control-IQ Low Alert occurs (indicating that the glucose is predicted to fall below 70 mg/dL within 15 minutes). Meal boluses will be supervised by study staff to ensure that the correct number of carbohydrate grams are entered into the bolus calculator.

At least one member of the study medical staff (Physician, NP) from will be present on site at all times. Up to 5 subjects will be studied at one time during the supervised phase. The goal of this

phase is to evaluate the safety of the system with correct and incorrect use of new features of the system.

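### Severe hypoglycemia and DKA are compared with a baseline that eligibility holds at zero, so the existing-versus-new display can show only no change or an increase

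*Combined protocol and SAP*

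**What the plan says.** Section 2.3 lists four primary safety endpoints: time below 54 mg/dL, severe hypoglycemia, DKA and serious adverse events (SAEs). Section 5.1 states that descriptive rates of "severe hypoglycemia, DKA, and serious adverse events will be reported for baseline and each intervention configuration". For severe hypoglycemia and DKA the statistics are the number of events and the percentage of subjects with at least one. For SAEs the statistic is a rate per 100 patient-years. Each subject is his or her own comparator, and the synopsis describes the evaluation as outcomes "after using existing Control-IQ system vs. new features".

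Three other provisions determine what the baseline column can contain:

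- Section 3.1.2 excludes, as separate criteria, "Diabetic ketoacidosis (DKA) in the past 6 months" and "Severe hypoglycemia (needing assistance) in the past 6 months".
- Section 4.4 says "Data from the 2-week period before enrollment will serve as the baseline pump and CGM data".
- Section 4.2 says "The subject will be considered enrolled when the investigator attests that the subject meets all eligibility criteria on the study enrollment CRF".

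Two passages do not fit these exactly. The synopsis merges the exclusions into one item: "Diabetic ketoacidosis (DKA) in the past 6 months and Severe hypoglycemia (needing assistance) in the past 6 months". Section 4.5.1 begins Phase 1 with "After enrollment and collection of baseline data (use of the current standard Control-IQ commercial system for 1-3 weeks", which can be read as a baseline that runs after enrollment. Table 1 likewise gives baseline on the standard system a column for Days -21 to 0.

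**The concern.** A baseline is useful as a comparator only if the event could have occurred in it at the rate that applies to the existing system. Here, anyone with a severe hypoglycemic or DKA event in the two baseline weeks would have been ineligible. The zero in the baseline column comes from the entry criteria and carries no information about current Control-IQ.

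Baseline is also the only existing-system period. In Table 4 it is the only row with standard Normal and Exercise settings and without Eating Soon or Late Bolus. Weeks A–D all turn exercise auto-bolus off and include Eating Soon. Week D restores the standard target but is still not the existing system. For these two endpoints, the existing-versus-new contrast therefore rests wholly on a period that cannot contain an event, and nothing in the plan says so.

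This matters because descriptive tables are the study's entire evidence. The primary objective is safety assessed by adverse event rates, and the synopsis says that the outcomes will guide the choice of features for later trials.

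**Working it through.** The documents give no background event rate, margin, power or sample-size derivation, so there is no planned figure to reproduce. The check has two parts.

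**1. Is the baseline count fixed?** The look-back is six months, about 26 weeks. The baseline is the last 2 of them (2/26 = 7.7%) and lies wholly inside. Enrollment requires all criteria to be met. Under Sections 3.1.2, 4.2 and 4.4 together, both counts are 0 of 30. The comparison can only tie or rise.

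**2. How much does this distort the display?**

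Inputs: up to 30 device wearers (Section 2.2), a 2-week baseline (Section 4.4), and four one-week configurations (Section 4.5.2, Table 4). Full enrollment and completion are assumed. The short Phase 1 stay is ignored.

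Person-time:
- baseline: 30 × 2 / 52.18 = 1.15 patient-years
- one configuration: 30 × 1 / 52.18 = 0.575 patient-years
- weeks A–D: 30 × 4 / 52.18 = 2.30 patient-years

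Let r be the combined rate of severe hypoglycemia and DKA per patient-year, *assumed* the same on the existing system and the new features, with Poisson counts.

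- Baseline fixed at zero: P(apparent increase) = 1 − exp(−2.30 r).
- Unselected baseline: the weeks A–D rate exceeds the baseline rate when the A–D count is more than twice the baseline count b. So P(apparent increase) = Σ_b Pois(b; 1.15 r) × P(Pois(2.30 r) > 2b).

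| Assumed rate per 100 patient-years | P(no baseline events) if unselected | P(increase), baseline fixed at 0 | P(increase), unselected baseline | Excess, points |
|---|---|---|---|---|
| 1 | 98.9% | 2.3% | 2.2% | under 0.1 |
| 5 | 94.4% | 10.9% | 10.3% | 0.6 |
| 10 | 89.1% | 20.5% | 18.3% | 2.2 |
| 20 | 79.5% | 36.9% | 29.5% | 7.4 |
| 50 | 56.3% | 68.3% | 42.1% | 26.2 |

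The last column is the part due to eligibility. The rest of the fourth column would arise with any two-week baseline of this size.

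One subject with one event would appear as 1/30 = 3.3% against 0%. That is weak evidence. Even with an unselected baseline and equal rates, a single event falls in the four study weeks rather than the two baseline weeks with probability 4/6 = 0.67. For two and three events, all fall in the study weeks with probability 0.67² = 0.44 and 0.67³ = 0.30.

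**The case against.** The strongest reply is that nothing turns on the baseline zero. The analysis is descriptive, with no test or margin. The individual-difference boxplots in Section 5.1 belong to the paragraph on glycemic outcomes, not events. Relatedness is judged event by event (Section 8.5), and the study-level stopping criterion is an absolute count (Section 8.13). A reader might infer that any study event will be read as harm from the new features. The documents do not support that, and this part of the reply stands in full. It does not make the baseline column informative.

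Second, small person-time limits the comparison more than eligibility does. This also stands: at assumed rates up to 10 per 100 patient-years, an unselected baseline would be zero 89% to 99% of the time. It would be wrong to attribute the whole 36.9% at 20 per 100 patient-years to the exclusion, because 29.5% would remain without it.

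Third, a reader might object to setting 14 baseline days beside 7 days per configuration. For severe hypoglycemia and DKA, a count fixed at zero is zero over either length. For SAEs, Section 5.1 already uses a rate per 100 patient-years. The window lengths add nothing here.

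Fourth, the zero may be less certain than it looks. Section 4.4 defines the two weeks for pump and CGM data and does not mention clinical events. The baseline questionnaire asks about the frequency of severe hypoglycemia and DKA with no stated look-back. The Table 2 footnote includes adverse event frequency at baseline. Section 4.5.1 and Table 1 leave room for baseline time after eligibility is attested. Read literally, the synopsis item excludes only subjects who had both events. These are fair points, but they show that the baseline for these endpoints is not clearly defined. Under the only explicit definition, in Section 4.4, the count is zero.

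Finally, any bias runs against the device, which is conservative for a safety aim. That lowers the severity. It does not turn the contrast into an estimate.

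**Conclusion.** The point holds as a biased display. Under Sections 3.1.2 and 4.4, baseline severe hypoglycemia and DKA are zero by eligibility and do not estimate the rate on current Control-IQ. The existing-versus-new comparison for these two primary endpoints can show only no change or an increase. No stopping or causality decision is affected.

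The added chance of a spurious increase is modest: about 2 points at 10, 7 at 20 and 26 at 50 per 100 patient-years, and under 1 point at 5 or below. These figures assume 30 completers, Poisson counts, one rate common to both periods, and a background rate that the documents do not supply.

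The point does not extend to time below 54 mg/dL, on which the exclusions place no such limit. It reaches SAEs only where the SAE is itself severe hypoglycemia or DKA. Severity is minor to moderate.

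**What to change.** In Section 5.1:

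1. State that baseline counts of severe hypoglycemia and DKA are zero by eligibility, and that change from baseline will not be interpreted for these two endpoints. Repeat this as a table footnote.
2. Report their weeks A–D events by configuration and pooled, with number of subjects, person-time and exact 95% intervals (Clopper-Pearson for the percentage of subjects, exact Poisson for the rate).
3. State that no week A–D is the existing system (Table 4). For these endpoints the trial then gives absolute study-period rates and descriptions between configurations, not an existing-versus-new contrast.

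Elsewhere, reconcile the baseline period in Section 4.5.1 (1–3 weeks, possibly after enrollment) and Table 1 (Days -21 to 0) with Section 4.4. Reconcile the combined exclusion item in the synopsis with the separate items in Section 3.1.2.

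The cost is one paragraph, a changed table shell and the wording reconciliation, with no new data. The sponsor gives up an existing-versus-new statement on these two endpoints, which the design cannot support.
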